The general objective of **Tech4D-Predict** is to develop methods for the acquisition and visualization of 4D human body models, aimed at supporting dietary-nutritional interventions and enhancing long-term patient motivation and adherence to treatment. Furthermore, the study will evaluate the impact of this tool on cognitive function and psychological well-being.

In pursuit of this overarching objective, the following specific aims are defined:

- **Specific Objective 1: Development of flexible methods for the acquisition of 3D human body models. The goal is to equip the acquisition system with flexibility, robustness, and portability without compromising accuracy.**

Flexibility refers to the system's ability to tolerate subject movements during the acquisition process, and even to leverage these movements to capture multiple views of the subject in order to complete the 3D model. The ultimate aim is to progress towards 3D self-portraits. Portability involves the ability to easily transport the system/device, using a compact set of RGB-D cameras integrated into a readily transportable device. Robustness refers to the stability of the acquisition system against potential movements that could affect camera calibration, as well as variations in acquisition conditions (e.g., lighting).

- **Specific Objective 2: Development of methods for obtaining multidimensional predictive models of morphological and clinical body evolution during dietary-nutritional treatment.**

The aim is to move beyond 4D memory-based models, which visualize the morphological changes experienced by the body during treatment, towards multidimensional predictive models that anticipate potential morphological changes and clinical outcomes for specific patient profiles. These predictions will be based on prior experience, the 4D morphological models of patients from the current project, and their corresponding clinical data.

- **Specific Objective 3: Evaluation of the effectiveness of multidimensional predictive model visualization on patient motivation during treatment and its impact on long-term adherence.**

The primary aim of this objective is to assess the impact of the methods developed in **Specific Objectives 1 and 2**—related to 4D model acquisition and visualization, and the construction of predictive models of clinical and morphological evolution—within a real clinical setting through a patient intervention.

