- Emotional Eating: Measured with the Emotional Eater Questionnaire (CCE) (Garaulet et al., 2012). Higher scores indicate greater influence of emotions on

food choices and eating habits.

- Prefrontal Symptoms: Assessed using the Prefrontal Symptoms Inventory (ISP-20) (Ruiz et al., 2012); the short version (Pedrero-Pérez et al., 2015) is a self-report questionnaire measuring cognitive, emotional, and behavioral alterations in daily activities.
- Impulsivity: Measured with the Barratt Impulsiveness Scale, BIS-II (Barratt, 1959), comprising 30 items divided into three subscales: cognitive impulsivity (8 items), motor impulsivity (10 items), and non-planning impulsivity (12 items).
- Health-Related Quality of Life: Assessed using the Short Form-12 Health Survey (SF-12) (Ware et al., 1996).
- Depression: Measured using the Beck Depression Inventory (BDI-II) (Beck, Steer & Brown, 1996).
- Life Satisfaction: Measured using the Satisfaction With Life Scale (SWLS) (Diener et al., 1985).

All questionnaire data were collected via Google Forms.

6. Technological and Body Image Variables

- **Body Image:** Assessed using the Body Self-Relations Questionnaire (MBSRQ – reduced Spanish version) (Botella et al., 2009). The instrument contains 45 items divided into two distinct parts: one evaluating general body image and another assessing satisfaction with specific body areas.
- **3D and 4D Images:** The 4D model represents morphological changes over time. Using wide-spectrum, low-cost 3D acquisition technologies (RGB-D sensors), a 4D model was constructed as the core of a human body visualization system, enabling accurate and realistic visualization over time. Throughout the intervention, morphological 3D images of participants were obtained, allowing them to observe their evolution through immersive Virtual Reality (VR) (only the experimental group observed these changes).

Morphological 4D images of participants in each session were captured using the 3D machine, composed of RGB-D devices for 3D image acquisition.

All anthropometric and clinical measurements were collected at the ALINUA Nutrition and Food Clinic, certified as a healthcare center affiliated with the Faculty of Health Sciences at the University of Alicante.

All questionnaires and the neuropsychological battery were administered at two time points: at the start of the program (initial session) and after six months of

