intervention. Anthropometric data and 4D images were also collected at both time points, as well as during individual follow-up sessions conducted to monitor progress and prevent relapses.

Monitoring Plan:

Potential adverse effects arising from the use of Virtual Reality (e.g., dizziness, discomfort, anxiety) and the dietary program (e.g., malnutrition, minor side effects) will be monitored. Adverse events will be recorded in a dedicated database and reported to the Ethics Committee if they are serious or unexpected. Participants will also have the right to withdraw from the study at any time without any consequences.

Data Analysis:

Data analysis is structured in two main phases, encompassing both the development of the predictive model and its clinical and psychological validation. A mixed strategy of advanced quantitative and computational analysis will be applied.

Data Preparation and Preprocessing

- Cleaning of clinical, anthropometric, psychological, and neuropsychological data.
- Standardization and normalization of variables (e.g., assessment scales, physical measurements).
- Coding of categorical variables (e.g., sex, experimental/control group).
- Outlier control and analysis of missing data (intent-to-treat analysis will be applied if missing data exceed 30%).

Classical Statistical Analysis

- **Between-group comparisons (control vs. experimental):**
 - t-tests or ANOVA for continuous measures.
 - Chi-square tests for categorical variables.
 - ANCOVA to adjust for covariates (age, sex, baseline BMI).
- **Longitudinal analysis:**
 - Repeated measures models (repeated measures ANOVA or mixed models).

- Study of changes between assessment points (0 and 6 months).

Multidimensional Predictive Modeling

- Use of multivariate regression models and machine learning to predict:
 - Body evolution (based on SMPL/STAR models).
 - Clinical parameters and psychological well-being.
 - Levels of adherence and motivation.
- Model training using data from the first period (M9) and validation in the second period.

Analysis of Predictive Psychological Variables

- Correlations between cognitive functions and adherence levels.
- Logistic/multiple regression analyses to identify significant predictors of therapeutic success.
- Evaluation of the mediating effect of psychological variables on physical and clinical changes.

Tools and Software

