- **Statistics:** IBM SPSS Statistics for Windows v.21.0 (IBM Corp, Armonk, NY; 2012), R (latest stable version), and Python 3.11.9 with SciPy and Statsmodels libraries.
- **Machine Learning and Predictive Modeling:** Scikit-learn for classical models and preprocessing. TensorFlow and PyTorch for developing deep learning models and neural networks, including generative networks (GANs) for 3D modeling and multidimensional analysis.
- **Visualization and Clinical Analysis:** Unity 3D for integration and immersive virtual reality visualization, Blender for 3D model manipulation and creation, and internally developed modules for project-specific VR systems.

Potential Limitations

- Possible selection bias (motivated volunteers).
- Loss to follow-up in a 6-month intervention.

- Limited generalizability to the Spanish population with specific sociodemographic characteristics.
- Risk of novelty effect with VR (results may reflect the appeal of the technology rather than the actual intervention effect).

7. Expected impact

In the ICT field, the project will provide methods and algorithms to advance the analysis and prediction of morphological evolution in relation to the parametric predictive model. Additionally, the challenge of acquisition using the RGB-D multi-camera column system and 3D self-portraits for home implementation introduces the development of new techniques based on sparse-view approaches.

In the Health Sciences, the project aims to evaluate the impact of predictive models on patient motivation and adherence to treatment for obesity and overweight. Special emphasis will be placed on the positive effect of realistic predictive visualization of individual body shape on cognitive functioning and psychological well-being.

Scientific and technical impact will be disseminated through presentations at international conferences (ECCV, CVPR, IJCNN in 2022; IUNS-ICN, ICCV in 2023) and publications in high-impact international journals starting in 2023 (IJCV, TPAMI, Pattern Recognition, ASOC, CVIU, EJCN, IJBNP, and JN). Results will also be shared in open-access repositories such as RUA. Data and results will be managed under privacy regulations (LOPDGDD and ENS) and made publicly available on open servers for use by the scientific community, with participants' consent. Developed methods will be shared on repositories such as Bitbucket. Results will also be published on the Tech4Diet website.

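### Specific Objective 3 names predictive-model visualization as what the trial tests, but the two-arm contrast as described cannot isolate its effect

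*Combined protocol and SAP*

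**What the plan says.** The combined protocol and SAP makes the claim in two places. Section 5 heads Specific Objective 3 "Evaluation of the effectiveness of multidimensional predictive model visualization on patient motivation during treatment", and extends it to adherence over the long term. Section 7 (Expected impact) says that "the project aims to evaluate the impact of predictive models on patient motivation and adherence to treatment for obesity and overweight".

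Section 5 also defines the difference that matters. Under Specific Objective 2: "The aim is to move beyond 4D memory-based models, which visualize the morphological changes experienced by the body during treatment", and the move is towards models that anticipate change. Section 6, item 2 (4D and Predictive Model Generation) draws the same line between looking back and projecting forward.

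On what participants saw, section 6 (Technological and Body Image Variables, 3D and 4D Images) says that 3D images were obtained during the intervention, "allowing them to observe their evolution through immersive Virtual Reality (VR) (only the experimental group observed these changes". Study Design defines the experimental arm as an individualized diet programme with 4D VR, and the control arm as nutrition and activity education.

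On the predictor, Specific Objective 2 says "These predictions will be based on prior experience, the 4D morphological models of patients from the current project, and their corresponding clinical data". The Data Analysis section adds "Model training using data from the first period (M9) and validation in the second period".

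**The concern.** The exposure named in the objective is not the exposure in the arm definition or the viewing procedure. If the plan is followed and a conclusion is drawn on Objective 3 as worded, a positive result would be reported as evidence that showing patients a predicted body improves motivation and adherence, and a null result would be held against that idea. Neither would follow, because the contrast does not isolate the forecast.

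This overlaps with the fact that the arms also differ in diet programme, but it is a separate gap. If both arms had received the same diet programme, it would still be undefined whether the VR sessions showed a forecast, a record of past change, or both.

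**Working it through.** No figure in the documents bears on this point, so the check sets the sections side by side and then asks what the contrast can identify.

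**1. Sections that name prediction as the thing evaluated**
- Section 5, Specific Objective 3 (heading).
- Section 7, the Health Sciences paragraph.

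**2. Sections that define the trial, its comparison or its procedures**
- Section 5, clinical trial under Objective 3: a personalized intervention of 4D modelling, VR and Mediterranean Diet treatment. None of the four trial-specific aims mentions prediction. The predictive model appears only as a recipient of trial data.
- Section 6, item 4 (Intervention Effect Analysis): Mediterranean Diet plus 4D VR models against conventional treatment, with the data then passed to the predictive models.
- Section 6, Study Design: individualized diet programme plus 4D VR against education.
- Section 6, 3D and 4D Images: the experimental group views its own evolution in VR. This matches what Specific Objective 2 calls memory-based.

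None of these gives a visit, frequency, time horizon or recipient for a forecast.

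**3. Sections that place prediction in the system**
- Section 3, Objective: the system offers VR views and personalized simulations, and the effect of the visualizations will be studied.
- Section 3, Method: the predictive system supports VR visualization meant to raise motivation.
- Section 6, opening sentence: the intervention uses tools that include predictive modelling.
- Section 6, item 2: a projection of the future body that may influence motivation.

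These describe capability and intent. They do not record delivery, but they conflict with reading group 2 as a complete account of what was shown.

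**4. Timing**
- The predictor rests partly on this project's patients and is trained on first-period data. The version trained on those data could not have been displayed before the data existed.
- Prior experience is also listed as a source, so some other version could have been available sooner.
- The two periods are not mapped to participants, visits or displays. Timing therefore limits one version of the model and settles nothing else.

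**5. What the contrast identifies**

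Suppose, for illustration only, that effects add. Let D be the effect of the individualized diet programme over education, V the effect of viewing one's own recorded evolution in VR, and F the average contribution of any forecasts shown. Then

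arm difference over 0 to 6 months = D + V + F.

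That is one estimable quantity and three unknowns. If no forecasts were shown, F = 0 and the trial says nothing about prediction. If every experimental participant saw forecasts, F is still inseparable from D and V. If some did, F is an average over an unstated share. In all three cases F is not identified. A larger sample would not change this.

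The listed analyses (t-tests, ANOVA, chi-square, ANCOVA on age, sex and baseline BMI, and repeated-measures models) include no variable for what was displayed.

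**The case against.** The strongest reply is that the documents do include prediction. The Summary and the opening of section 6 describe it as part of the system and the intervention. The sentence on viewing sits among data-collection variables and is not a full specification of the intervention; its restriction concerns which arm viewed, not what was shown. Objective 3 is also broader than its heading. Its text begins "The primary aim of this objective is to assess the impact of the methods developed in" and goes on to name Specific Objectives 1 and 2, so 4D acquisition and visualization are included, and the trial aims already describe a package. Section 7 is a project-level statement.

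Most of this stands, and it rules out some stronger readings that a reader might infer:

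- *That no participant saw a forecast, or that prediction is absent from the package.* This is an inference from silence, and the Summary and section 6 point the other way.
- *That the predictor was built only from this trial's data, so no forecast could have existed in time.* Specific Objective 2 also lists prior experience, and trial data are said to improve the model, which is compatible with a model that already existed.
- *That the intervention changed part-way, diluting the effect by a calculable amount.* The periods are not tied to participants and no share is given. Such a calculation would also have to assume that viewing past change has no effect, whereas section 4 argues that images of progress help adherence.

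The reply does not rescue the claim. Intent to include forecasts does not define an exposure, and the breadth of Objective 3 is a reason to word its conclusion as a package effect.

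**Conclusion.** The concern holds in this form: the protocol names predictive-model visualization as what is evaluated, its trial-level text describes a diet programme plus 4D VR of the participant's own evolution, and it leaves unstated whether, when or to whom forecasts were shown. As written, the two-arm contrast cannot isolate an effect of predictive visualization.

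No numerical size can be attached, because the documents give no exposure share. The reach is clear: it covers any efficacy statement specific to prediction, in either direction. It does not touch the comparison of the combined programme with education, or the technical evaluation of the predictor under Objective 2.

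The conclusion rests on Study Design giving the true difference between the arms, and on no display specification existing elsewhere in the plan. It does not depend on whether forecasts were in fact shown.

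**What to change.** 1. Reword the conclusion to be drawn under Specific Objective 3, and the matching sentence in section 7, as the effect of the combined programme (individualized Mediterranean Diet intervention plus 4D VR viewing) versus education. State that no efficacy claim, positive or null, will be made for predictive visualization on its own.
2. Keep the building and validation of the predictor under Specific Objective 2.
3. Reconcile section 3, Specific Objectives 2 and 3 with the trial aims, section 6 (opening, items 2 and 4, Study Design, 3D and 4D Images) and Data Analysis on what was displayed, at which sessions and to whom. Say how the first period (M9) and the second period relate to participants.
4. If records show that some participants saw forecasts, report that exposure descriptively. The documents do not say that displayed content was logged, so this step is conditional. Splitting the comparison by period would not isolate prediction either, since the arms would still differ in diet programme.

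The cost is a few sentences of rewording and one check of whatever records exist. The real price is that the trial gives up a claim specific to prediction, which is the most novel one the protocol makes.

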Objective: The main objective of this research project is to develop a 4D visual representation model of the human body that allows the analysis of morphological changes resulting from obesity treatment. This 4D model will serve as the core of a body visualization system aimed at improving obesity treatment. The system will provide immersive virtual reality visualizations and personalized simulations of body

evolution during treatment. Furthermore, the effect of these realistic visualizations on patient motivation and adherence to treatment will be studied.

Method: The proposed methodology for obtaining the morphological change representation model presents a significant research challenge. The multidisciplinary intervention combines clinical, psychological, and technological assessments in patients with overweight or obesity. The body is captured in 3D using RGBD sensors to create complete body models, and 4D models reflecting morphological changes over time are generated using advanced deformable registration techniques. These models feed a predictive system that anticipates body evolution under different dietary-nutritional scenarios, facilitating immersive virtual reality visualizations to improve motivation and adherence.

A longitudinal study design is proposed, with two groups (experimental and control) and evaluations at baseline and after six months. Clinical, anthropometric, psychological, nutritional, and technological data will be collected using validated questionnaires and precise measurements.

The analysis includes health indicators, cognitive functions, emotional well-being, and adherence, aiming to validate the system and its impact on motivation and clinical outcomes. Both classical and advanced statistical analyses will be performed, combining traditional methods (t-tests, ANOVA, regressions) with machine learning to predict body evolution, clinical parameters, and adherence. Sample losses will be controlled, and psychological variables will be evaluated as predictors of therapeutic success. Tools such as SPSS, R, Python, TensorFlow, PyTorch, Unity 3D, and Blender will be used.

4. Antecedentes, planteamiento del problema, justificación de la investigación

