Accordingly, this objective encompasses the implementation of a clinical trial **with two intervention groups (experimental and control)** designed to evaluate the effect

of a personalized intervention combining the benefits of 4D body modeling and virtual reality techniques with a dietary-nutritional treatment based on the Mediterranean Diet. The intervention aims to enhance motivation for change, treatment adherence, and health parameters in overweight and obese patients.

Furthermore, this study will allow systematic collection of clinical, anthropometric, nutritional, and psychological data, which will be integrated into the multidimensional predictive model to improve its precision and personalization capabilities.

Specifically, the clinical trial includes the following specific aims:

- To study how a 4D computer vision model combined with virtual reality technology can improve clinical assessment, the analysis of temporal morphological changes of the human body, and adherence to dietary-nutritional treatment.
- To evaluate whether adherence to an intensive multifactorial dietary-nutritional treatment based on the Mediterranean Diet, supported by immersive 4D virtual reality technology, leads to improvements in cognitive functioning.
- To analyze the impact of a nutritional intervention program based on the Mediterranean Diet and the use of virtual reality on body image perception.
- To determine whether a combined intensive intervention—based on the Mediterranean Diet and 4D virtual reality technology—can improve patients' overall health.

6. Methodology

The intervention follows a multidisciplinary approach that combines clinical, psychological, and technological assessment of overweight or obese patients, using innovative tools based on 3D body reconstruction and predictive modeling.

Challenges to Address and Technical Phases

1. 3D Model Acquisition

3D images of the body are captured from multiple viewpoints using RGB-D sensors, due to their precision, low cost, and portability. The images are aligned using articulated rigid registration techniques, enabling the construction of a complete body model. The research team has developed advanced RGB-D camera alignment methods, optimizing accuracy under real-world capture conditions [22–24].

2. 4D and Predictive Model Generation

Starting from 3D models obtained at different stages of the treatment, deformable

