registration techniques (such as CPD or TPS-RPM) are applied to quantify morphological deformations. These variations are parametrically represented using methods such as *Relative Elemental Growth Rate* or *GRID*, facilitating temporal analysis of body changes [27–31]. Additionally, a predictive model of body shape and texture is developed, conditioned on dietary-nutritional and psychological variables. This model allows anticipation of the patient's body evolution under different intervention scenarios, moving from a retrospective view to a future projection that can directly influence motivation.

3. 3D and 4D Model Visualization

The models are processed to generate realistic visualizations compatible with low-cost virtual reality devices. Solid surfaces are reconstructed from point clouds using specific geometric modeling techniques [32, 33]. The team has prior experience in advanced visualization in sectors such as footwear manufacturing and automated visual inspection. Multidimensional model visualization not only provides a clearer understanding of physical changes but also aims to generate a positive emotional impact on the patient. This personalized virtual representation of body evolution serves as a motivational reinforcement to maintain long-term adherence.

4. Intervention Effect Analysis

The effect of the system on motivation, treatment adherence, cognitive function, and psychological well-being will be assessed. An intensive intervention based on the Mediterranean Diet combined with 4D VR models will be compared to conventional treatment. Collection of clinical, anthropometric, and psychological data will allow system validation and feed the predictive models. Patient health will be monitored through indicators such as weight, BMI, body fat percentage, adipose tissue distribution, cardiovascular risk indicators, and metabolic syndrome parameters. Additionally, questionnaires assessing emotional, motivational, and cognitive status, as well as body image perception and executive function—which is related to the ability to maintain long-term healthy behaviors—will be included.

Technical Capacity and Team Experience

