The project is multidisciplinary, with multiple disciplines collaborating to achieve the common goal of improving motivation and long-term adherence to dietary-nutritional treatments. The research team has a strong track record in 3D image capture and processing, RGB-D sensor calibration and registration [22–27], as well as realistic modeling and visualization. The team also includes professionals in nutrition, psychology, and clinical assessment with experience in national and European projects focused on obesity, treatment adherence, and mental health.

Ethical Considerations

The study was approved by the Research Ethics Committee of the University of Alicante (code UA-2021-11-18, dated 18/11/2021). Prior to study participation and data collection, all participants provided written informed consent. Data will be handled in accordance with the GDPR and LOPDGDD regulations, with anonymization implemented through unique participant codes.

The following sections describe the study design, selected population, eligibility criteria, sampling strategy, sample size calculation, definition of included variables, measurement instruments, monitoring plan, and analysis strategies, along with potential limitations.

Study Design

A prospective longitudinal design with two assessment points was implemented: baseline (pretest) and post-intervention (posttest) after six months of treatment. The study comprised two groups: control and experimental. The control group received nutritional and physical activity education based on recommendations from a nutritionist. The experimental group received a specific, individualized dietary-nutritional intervention program combined with 4D virtual reality. Both groups were assessed for cognitive, clinical, and nutritional outcomes at baseline (pretest) and after six months of intervention (posttest).

To ensure sample representativeness and the generalizability of results, the sample size was calculated using the G*Power 3.1 statistical software. A statistical power of 80%, a medium effect size (0.5), and a significance level (α) of 0.05 were established. Under these parameters, at least 35 participants per group were required to carry out the intervention.

Selected Population

The sample consisted of a total of 133 Spanish volunteers, both men and women, aged between 22 and 67 years ($M = 47.11$ years; $SD = 9.38$). Participants were randomly assigned to one of the two groups (experimental or control).

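### Specific Objective 3 names an effect of the visualization, but the arms also differ in dietary programme and education, so only the effect of the whole package can be estimated

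*Combined protocol and SAP*

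**What the plan says.** All references are to the combined protocol and SAP.

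**What each arm received.** Under Study Design (section 6): "The experimental group received a specific, individualized dietary-nutritional intervention program combined with 4D virtual reality". For the comparator: "The control group received nutritional and physical activity education based on recommendations from a nutritionist". Physical-activity education is described for controls and is not described for the experimental arm. Technological and Body Image Variables (section 6) says of the body images that they were obtained from participants, "allowing them to observe their evolution through immersive Virtual Reality (VR) (only the experimental group observed these changes". The restriction is on viewing; imaging is not limited to one arm.

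**What is compared.** Classical Statistical Analysis (section 6) lists "Between-group comparisons (control vs. experimental" with t-tests or ANOVA, chi-square tests and ANCOVA on age, sex and baseline BMI, followed by repeated-measures models.

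**Where the target is the package.** The sentence in section 5 that introduces the clinical trial describes "a personalized intervention combining the benefits of 4D body modeling and virtual reality techniques with a dietary-nutritional treatment based on the Mediterranean Diet". Intervention Effect Analysis (section 6) says: "An intensive intervention based on the Mediterranean Diet combined with 4D VR models will be compared to conventional treatment".

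**Where the target is the technology.** The summary objective (section 3) says that "the effect of these realistic visualizations on patient motivation and adherence to treatment will be studied", and the summary of the analysis describes it as "aiming to validate the system and its impact on motivation and clinical outcomes". The general objective (section 5) speaks of the impact of the tool. The heading of Specific Objective 3 names the effectiveness of predictive-model visualization for motivation and adherence. The first trial aim names 4D modelling with VR as improving adherence, among other things. Intervention Effect Analysis opens with what the system does to motivation, adherence, cognition and well-being. Section 7 names the impact of the predictive models and of the visualization.

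**Limitations.** Potential Limitations (section 6) lists a novelty effect of VR. It does not say that the arms differ in anything other than VR.

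**The concern.** The document states two targets for one randomised comparison. One is the effect of a package: dietary programme plus VR viewing. The other is the effect of one part of it, the visualization. The arms were built for the first, while Specific Objective 3, which the trial is there to serve, is worded as the second.

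The risk arises at reporting. If the results are written up against Specific Objective 3, a difference that came partly or wholly from the individualized dietary programme could be credited to the visualization or the predictive models. Section 7 plans patents, an assessment of a possible company and transfer to healthcare institutions, so it matters which component gets the credit.

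**Working it through.** **Inputs.** Two arms, their contents and the total of 133 participants come from section 6 (Study Design and Selected Population). VR viewing in one arm only comes from Technological and Body Image Variables. The split of the 133 by arm is not given; 66.5 per arm is assumed.

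**Step 1: what the contrast contains.** Write the expected outcome in each arm as a common level *m* plus the effects of what that arm received:

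- Control: *m* + *a*, where *a* is the effect of the nutrition and physical-activity education.
- Experimental: *m* + *p* + *v* + *i*, where *p* is the effect of the individualized dietary programme, *v* that of VR viewing and *i* their interaction.

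Experimental minus control = *p* + *v* + *i* − *a*. The visualization objectives ask about *v* (or *v* + *i*). The data give the sum only.

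**Step 2: can it be separated?** Leave out *a* and *i*, the case most favourable to the plan. With columns (intercept, programme, VR), the rows are control (1, 0, 0) and experimental (1, 1, 1). The last two columns are identical, so the rank is 2 for 3 parameters. More participants repeat the same two rows and leave the rank at 2. An arm with the programme and no VR viewing would add the row (1, 1, 0) and bring the rank to 3; no such arm exists.

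**Step 3: do the planned analyses help?**

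- Age, sex and baseline BMI are baseline covariates. Adjusting for them does not separate programme from VR.
- The group-by-time term in a repeated-measures model is again the contrast between the same two arms.
- Mediation by psychological variables asks how an effect travels, not which component caused it. Using it, or within-arm VR exposure, to isolate VR would need assumptions that the data cannot test.

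**Step 4: what misattribution could look like (illustration).** Assume *v* = *i* = 0 and let *p* − *a* give a standardised difference *d*. The probability of a significant two-sided t-test at 0.05 follows from the noncentrality *d*√(*n*/2), with *n* per arm and no dropout:

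| *d* (assumed) | *n* = 66.5 | *n* = 35 |
|---|---|---|
| 0.5 | 0.5 × √33.25 = 2.88, about 82% | 0.5 × √17.5 = 2.09, about 54% |
| 0.25 | 0.25 × √33.25 = 1.44, about 30% | 0.25 × √17.5 = 1.05, about 18% |

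The 35 is the plan's stated minimum per group. At its stated inputs (80% power, effect size 0.5, α 0.05), an unadjusted two-sided t-test needs 64 per group, so that test does not reproduce 35. That is a separate matter, and Steps 1 to 3 do not depend on it.

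**The case against.** The strongest reply is that the operative text already describes the package. Specific Objective 3 is followed at once by a trial of a combined intervention, and the sentence about the system is followed by the package comparison. Much of the technology wording sits in summary or impact text, and some of it (validating the system, improving clinical assessment) is partly technical. Package trials are legitimate, and the novelty limitation shows that attribution was considered.

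Most of this is fair as far as it goes. It narrows the point to the motivation, adherence, cognition and well-being claims and leaves the technical aims alone. But describing the package does not withdraw the visualization objective, which still stands as the heading. The novelty limitation asks whether VR's appeal drives the result, not whether the diet programme does.

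Four stronger readings are tempting, and the documents do not support them.

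- *The comparison is invalid.* It is not: assignment was random, and the package contrast answers a proper question.
- *The number of technology sentences measures the problem.* Many restate one objective, so a count says nothing about size.
- *All trial aims other than the first already state the package effect.* The second does not. Its exposure is adherence to the combined treatment, which arises after randomisation, so the arm comparison does not estimate it.
- *The arms differ in exactly two things.* Physical-activity education is described for controls only, and the VR difference is in viewing, not imaging. The variables section says that participants viewed their own evolution; it does not say that they were shown predictions.

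**Conclusion.** The point holds. The randomised comparison estimates the six-month effect of the whole package against control education. It cannot estimate the effect of the visualization, the system or the predictive models named in Specific Objective 3 and the matching statements.

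The size is structural: one contrast for at least two components, with no arm receiving one without the other. It rests only on the arm descriptions. The percentages are illustrations that also assume the effect sizes, an equal split, no dropout and a zero VR effect; they are not a forecast. Nothing in the plan says that a difference will be credited to VR, so the harm is conditional on how results are reported. This should be fixed, but it does not undermine the trial.

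**What to change.** 1. State the randomised conclusion as: *the six-month effect of the combined package (individualized Mediterranean-diet programme plus 4D/VR viewing) versus control education*.
2. Reword Specific Objective 3, the adherence clause of the first trial aim and the opening sentence of Intervention Effect Analysis to match. Bring the general objective, the two summary statements and the section 7 restatements into line. The sentence introducing the trial, the package comparison sentence and the technology-development aims can stay.
3. Label any analysis of the visualization component as exploratory.
4. Describe the second aim's adherence-to-cognition question as a non-randomised association, outside the package contrast.
5. Add to Potential Limitations: *The arms differ in the dietary programme, in the education provided and in VR viewing, so a between-group difference cannot be attributed to the visualization alone.*

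The cost is wording: no new participants, data or analyses. The real price is that the trial cannot claim from its randomised comparison that visualization itself improves motivation, adherence or well-being. Such a claim would need a comparator with the same dietary programme and no VR viewing. Recruitment is described in the past tense, so this point does not ask for one.
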